8.4.4 Mood Disorders (e.g. Anxiety, Depression, Agitation)

Worst Toxicity*	Management
Grade 1 or grade 2 without increase in GAD7/PHQ9 scores from baseline	Maintain dose level. Consider psychiatric consultation at the investigator's discretion and introduce optimal management.
Grade 2 with increase in GAD7/PHQ9 scores from baseline	Omit dose until resolved to \leq Grade 1 or baseline status. Consider psychiatric consultation at the investigator's discretion and introduce optimal management**. First event: if the condition resolves to Grade \leq 1 or to baseline status, continue to co-medicate and then maintain the dose level. Second and further events: if the condition resolves to Grade \leq 1 or to baseline status, continue to co-medicate and then decrease 1 dose level.
Grade 3	Omit dose until resolved to \leq Grade 1 or baseline status, then decrease one dose level***. Co-medicate**. Psychiatric referral recommended.
Grade 4	Discontinue buparlisib Urgent psychiatric referral
Suicidal ideation regardless of grade	Interrupt buparlisib. Refer for psychiatric consultation for optimal management and to confirm if study drug should be interrupted or permanently discontinued. In this specific case, the psychiatric advice can overrule the patient's PHQ-9 self-assessment.

* See Section 8.3.
 
** Under the guidance of the psychiatrist if needed. Possible first line management for anxiety might include lorazepam (e.g. 0.5 mg po tid), clonazepam (e.g. 1 mg po bid) or haloperidol (0.5-1 mg po bid). Options for first line treatment of depression might include citalopram (e.g. starting doses 10-20mg, usual treatment dose 20-60 mg/d). In the event of agitation interrupting sleep, consider trazodone (e.g. 25 to 50 mg at night).
 
*** After treatment is resumed at a lower dose, if the same toxicity recurs with the same severity, then the next treatment should be resumed at a lower dose regardless of duration. If the same toxicity occurs with a worse severity, then the patient must discontinue treatment with buparlisib.
 
If a third dose reduction is required, patients must discontinue protocol therapy.
 
If therapy is delayed by > 28 days, patients must discontinue protocol therapy.
	

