- Score of ≥ 12 on the PHQ-9 questionnaire (posted on IND 216 website)
- Score of ≥ 15 on the GAD-7 mood scale (posted on IND 216 website)
- \geq CTCAE Version 4.0 grade 3 anxiety
- Patient selects a positive response of '1,2,3' to question 9 (suicidal ideation) in the PHQ-9 questionnaire

5.2.8 Patients who have received prior buparlisib (BKM120).

5.2.9 Patients with impairment of gastrointestinal (GI) function or GI disease that may significantly alter the absorption of buparlisib (e.g. ulcerative diseases, uncontrolled nausea, vomiting, diarrhea, malabsorption syndrome, or small bowel resection).

5.2.10 Patients who are unable to swallow capsules.

5.2.11 Patients on strong CYP3A inhibitors/inducers or therapeutic doses of warfarin-like anticoagulants (must have discontinued ≥ 7 days prior to day 1). Patients may receive low molecular weight heparin if indicated. See Appendix VII for a list of prohibited medications.

5.2.12 Patients on drugs with a known risk to induce Torsades de Pointes (see Appendix VIII).

5.2.13 Patients receiving high dose steroid therapy or another immunosuppressive agent. Note: Topical applications (e.g. rash), inhaled sprays (e.g. obstructive airways diseases), eye drops or local injections (e.g. intra-articular) are allowed. Patients who are on stable moderate dose corticosteroid treatment for treatment of conditions other than CLL (\leq dexamethasone 4 mg/day, prednisone 25 mg/day) for at least 14 days before start of study treatment are eligible.

5.2.14 Patients with known HIV positivity.

5.2.15 Patients with known CLL involvement of the central nervous system.

AMEND #1: 2015-OCT-22; AMEND #3: 2016-AUG-24

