8.6 Concomitant Therapy

Permitted:

- Other supportive and palliative care (e.g. pain control) as required throughout the study.
- Anti-emetics or anti-diarrheal agents as required.
- Growth factors may be used according to centre policy.
- Low molecular weight heparin if indicated.

Permitted with caution:

- CYP450 substrates other than strong CYP3A4 inhibitors and inducers (see Appendix VII).
- Drugs with possible or conditional risk of inducing Torsades de Pointes (see Appendix VIII).

Not permitted:

- Strong CYP3A4 inhibitors and inducers (see Appendix VII).
- Drugs with known risk to induce Torsades de Pointes (see Appendix VIII).
- Warfarin.
- Other anti-cancer therapy or investigational therapy.

Details of any concomitant medications given should be recorded on the appropriate Electronic Case Report Form.

Infections including Pneumocystis Jiroveci pneumonia (PJP) and cytomegalovirus (CMV) reactivation have been observed in patients with CLL treated with alternate PI3 kinase inhibitors. Opportunistic infections have not been associated with buparlisib therapy to date. Physicians should remain vigilant and investigate as clinically appropriate in event of fever or respiratory symptoms. Prophylaxis can be considered in those at high risk at investigator discretion.

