APPENDIX VIII - QT PROLONGING DRUGS

Updates to this list will be published on the trial website.

List of prohibited QT prolonging drugs with known risk of Torsades de Pointes

Drug	QT risk(*)	Comment
Amiodarone	Known risk for TdP	Females>Males, TdP risk regarded as low
Arsenic trioxide	Known risk for TdP	
Astemizole	Known risk for TdP	No Longer available in U.S.
Bepridil	Known risk for TdP	Females>Males
Chloroquine	Known risk for TdP	
Chlorpromazine	Known risk for TdP	
Cisapride	Known risk for TdP	Restricted availability; Females>Males.
Disopyramide	Known risk for TdP	Females>Males
Dofetilide	Known risk for TdP	
Domperidone	Known risk for TdP	Not available in the U.S.
Droperidol	Known risk for TdP	
Halofantrine	Known risk for TdP	Females>Males
Haloperidol	Known risk for TdP	When given intravenously or at higher-than- recommended doses, risk of sudden death, QT prolongation and torsades increases.
Ibutilide	Known risk for TdP	Females>Males
Levomethadyl	Known risk for TdP	
Mesoridazine	Known risk for TdP	
Methadone	Known risk for TdP	Females>Males
Pentamidine	Known risk for TdP	Females>Males
Pimozide	Known risk for TdP	Females>Males
Probuconol	Known risk for TdP	No longer available in U.S.
Procainamide	Known risk for TdP	
Quetiapine	Possible risk for TdP	Prohibited as this drug is a sensitive 3A4 substrate
Quinidine	Known risk for TdP	Females>Males
Sotalol	Known risk for TdP	Females>Males
Sparfloxacin	Known risk for TdP	
Tacrolimus	Possible risk for TdP	Prohibited as this drug is a sensitive 3A4 substrate with narrow TI
Terfenadine	Known risk for TdP	No longer available in U.S.
Thioridazine	Known risk for TdP	
Vardenafil	Possible risk for TdP	Prohibited as this drug is a sensitive 3A4 substrate
(*) Classification according to the Qtcdrugs.org Advisory Board of the Arizona CERT Sensitive substrates: Drugs whose plasma AUC values have been shown to increase 5-fold or higher when co-administered with a potent inhibitor of the respective enzyme.		
Note: drugs with a known risk for TdP that are also strong inhibitors of CYP3A are not repeated here and only mentioned in Table 1.		

List of QT prolonging drugs to be used with caution

Updates to this list will be published on the trial website.

Drug	QT risk (*)
Alfuzosin	Possible risk for TdP
Amantadine	Possible risk for TdP
Amitriptyline	Conditional risk for TdP
Azithromycin	Possible risk for TdP
Chloral hydrate	Possible risk for TdP
Citalopram	Conditional risk for TdP
Clomipramine	Conditional risk for TdP

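### Section 8.4.4 offers oral haloperidol for anxiety, although Section 8.6 and Appendix VIII prohibit it without exception

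*Protocol*

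**What the plan says.** Section 8.4.4 of the Protocol sets out how to manage mood toxicity. Its footnote ** begins the anxiety options with "Possible first line management for anxiety might include lorazepam (e.g. 0.5 mg po tid") and continues with "clonazepam (e.g. 1 mg po bid) or haloperidol (0.5-1 mg po bid"). The footnote is attached to two rows of the table: grade 2 with a rise in the GAD-7 or PHQ-9 score, and grade 3. Buparlisib is withheld in both. In the grade 2 row, once a first event has resolved, the instruction is to "continue to co-medicate and then maintain the dose level".

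Section 8.6 lists, under treatments that are not permitted, "Drugs with known risk to induce Torsades de Pointes (see Appendix VIII"). Section 5.2.12 uses the same class of drugs as an entry exclusion: "Patients on drugs with a known risk to induce Torsades de Pointes (see Appendix VIII").

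Appendix VIII has a table titled "List of prohibited QT prolonging drugs with known risk of Torsades de Pointes". Haloperidol is a row of that table, classed as known risk, with the comment "When given intravenously or at higher-than- recommended doses, risk of sudden death, QT prolongation and torsades increases".

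**The concern.** Two current instructions in one protocol cannot both be followed for this drug: the toxicity table suggests it and the concomitant-therapy rule bars it. The footnote does not point to Section 8.6 or Appendix VIII, so a prescriber working from the toxicity table, who may be a consulting psychiatrist, has no prompt to check.

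The setting is not remote. Section 8.4 lists mood alterations among the most frequent buparlisib toxicities. The GAD-7 entry exclusion in Section 5.2.7 starts at 15, so patients scoring 10 to 14, which Section 8.3 grades as grade 2 anxiety, are not excluded on that score.

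At stake are patient safety and protocol compliance. The 12-lead ECG is scheduled before registration, and Appendix I then leaves it to clinical indication, so starting haloperidol does not itself trigger one.

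**Working it through.** The only arithmetic is the ceiling on patients. The rest is a comparison of the text.

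1. **What is suggested.** Footnote ** of Section 8.4.4 names haloperidol 0.5-1 mg by mouth twice daily as the third of three options for anxiety. The wording is permissive.

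2. **What is prohibited.** Section 8.6 bars known-risk Torsades drugs and defines them by Appendix VIII. Appendix VIII classes haloperidol as known risk and places it in the prohibited table. The category that Section 8.6 permits with caution covers only possible or conditional risk, so haloperidol does not fall there. The readable caution list in Appendix VIII breaks off early in the alphabet, but the prohibited entry settles the drug's status.

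3. **Is there a dose or route exception?** The haloperidol comment says when risk rises. It does not say that use is allowed at other times. The amiodarone row in the same table carries the comment "TdP risk regarded as low", yet amiodarone stays prohibited. For quetiapine, tacrolimus and vardenafil the comment explains why the drug is barred. Where this protocol wants an exception, it writes one: Section 5.2.13 allows stable corticosteroids up to stated milligram limits, along with topical and inhaled forms, and Section 5.2.11 allows low molecular weight heparin. There is no similar text for haloperidol.

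4. **Is there an exception while buparlisib is held?** None is stated in Sections 8.4.4 or 8.6 or in Appendix VIII. In any case the grade 2 row continues co-medication when buparlisib resumes, both after a first event (same dose) and after later events (one level lower). The grade 3 row calls for co-medication and resumption one level lower, and does not say when co-medication ends.

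5. **How many patients could be affected?** Section 14.2 gives 12 patients in the PI3K-inhibitor-naive cohort and at most 17 in the exploratory cohort: 12 + 17 = 29. This is a ceiling on the whole trial. The documents give no rate of anxiety treatment or of haloperidol use, so no expected count can be derived.

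6. **Effect on the statistics.** The response criteria, the two-stage rule, the sample size and the SAP outputs do not depend on this point.

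**The case against.** The strongest reply concerns weight. The footnote only suggests, two benzodiazepines come before haloperidol, and a site can comply with every section by choosing one of them. Exposure needs a chain of events: haloperidol is chosen, the event resolves, and the drug is continued when buparlisib restarts. Continuation is explicit only for grade 2; for grade 3 it is inferred from silence.

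There are also real safeguards:

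- The footnote provides for psychiatric guidance if needed. Consultation is to be considered at grade 2, and referral is recommended at grade 3.
- Entry criteria exclude specified mood disorders and significant cardiovascular disease (Sections 5.2.6 and 5.2.7) and require normal potassium and calcium (Section 5.1.7).
- Section 9.1 repeats potassium and calcium on days 1 and 14 of cycles 1 and 2, then on day 1 of each cycle.
- An ECG may be done when clinically indicated, and starting a QT-prolonging drug is an obvious occasion.
- Concomitant drugs are recorded on the case report form.

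In addition, Section 5.2.12 governs entry only, so it is not a second contradiction. It shows that the ban is consistent elsewhere. Updates to the Appendix VIII list are posted on the trial website and cannot be seen here, so the absence of an exception can be stated only for the readable text.

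All of this stands, and it is why the expected effect is small. It does not remove the conflict: none of these points makes haloperidol permitted, and recording its use does not prevent it.

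**Conclusion.** The concern holds. Section 8.4.4 offers a drug that Section 8.6 and Appendix VIII prohibit, and the readable text contains no exception for low oral doses or for dose holds. Few patients, possibly none, would be affected, and in no case more than 29. The documents give no data on buparlisib's own QT effect, so the added risk at 0.5-1 mg by mouth cannot be quantified. This is a conduct and safety inconsistency with no effect on any endpoint or statistical result. It should be corrected because the protocol itself classes the drug as known risk and because overlap with resumed buparlisib is foreseeable. The conclusion assumes that the web version of the Appendix VIII list has not removed haloperidol or added an exception.

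**What to change.** First check the current web version of the Appendix VIII list. If haloperidol is still prohibited, delete it and its dose from footnote ** of Section 8.4.4, leaving lorazepam and clonazepam, and notify sites. A short pointer from the footnote to Section 8.6 and the drug appendices would be a useful addition, but the correction does not depend on it.

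If the sponsor's safety team does intend to allow low-dose oral haloperidol, it should instead write that exception, with dose and route, into Section 8.6 and Appendix VIII, and require an ECG when the drug is started.

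Either way the cost is a short amendment or clarification memo, with no change to sample size or analysis. The second route also adds an ECG for each patient who starts the drug.

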8.4.5 Hyperglycemia

Fasting plasma glucose (FPG)	Management *
Grade 1	Maintain dose level Check FPG at least weekly for 8 weeks, then at least every 2 weeks
Grade 2	If signs or symptoms of hyperglycemia (e.g. mental status changes, excessive thirst, polyuria) manage as per grade 3 below If asymptomatic, maintain dose and recheck FPG in 24 hours. If grade worsens or improves follow specific grade recommendations. If remains at grade 2: 
 Maintain dose level and monitor FPG at least weekly until resolves to \leq grade 1 Initiate or intensify appropriate anti-diabetic treatment** such as metformin; consider adding a second oral agent if no improvement after several days If FPG does not resolve to \leq grade 1 within 14 days after institution of anti-diabetic treatment, reduce buparlisib by one dose level*** Continue with anti-diabetic treatment and check FPG at least weekly for 8 weeks, then continue checking at least every 2 weeks
Grade 3	Omit buparlisib, initiate or intensify medication with anti-diabetic therapy, recheck FPG within 24 hours. If grade worsens or improves follow specific grade recommendations. If remains at grade 3: 
 Continue to omit buparlisib Monitor FPG at least twice weekly until resolves to \leq grade 1 If FPG resolves to \leq grade 1 in 7 days or less then restart buparlisib and decrease one dose level *** If FPG remains greater than grade 1 severity for more than 7 days, then discontinue buparlisib Continue oral anti-hyperglycemic therapy** such as metformin as appropriate Check FPG weekly for 8 weeks, then every 2 weeks
Grade 4	Omit buparlisib, initiate or intensify medication with appropriate anti-diabetic treatment, re-check within 24 hours. If grade improves then follow specific grade recommendations. If FPG is confirmed at Grade 4: 
 discontinue buparlisib check FPG at least weekly for 8 weeks, then at least every 2 weeks until resolved

* At any grade give appropriate dietary advice
 
** Some oral anti-diabetic drugs are CYP2C9 substrates (glipizide, glimepiride, gliclazide, glibenclamide, nateglinide, rosiglitazone) and should be used with caution. See Appendix VII.
 
*** If a third dose reduction is required, patients must discontinue protocol therapy. If therapy is delayed by > 28 days, patients must discontinue protocol therapy.
	

8.4.6 Interstitial Pneumonitis

Symptoms suggestive of pneumonitis require evaluation and investigation with CT imaging and bronchoscopy as clinically appropriate.

Worst Toxicity	Management*
Grade 1	Maintain dose level
Grade 2	Reduce by one dose level** and continue therapy OR Omit buparlisib if symptoms are troublesome. If resolved to \leq grade 1 within 28 days, may restart at a reduced dose level.
Grade 3	Omit dose until resolved to \leq grade 1. May restart buparlisib within 28 days at a reduced dose level**, if evidence of clinical benefit.
Grade 4	Discontinue buparlisib

* Consider corticosteroids if symptoms troublesome and infective origin excluded (patients requiring high dose steroids may become inevaluable for response assessment)

** After treatment is resumed at a lower dose, if the same toxicity recurs with the same severity, then the next treatment should be resumed at a lower dose regardless of duration. If the same toxicity occurs with a worse severity, then the patient must discontinue treatment with buparlisib.

If a third dose reduction is required, patients must discontinue protocol therapy.

If therapy is delayed by $>$ 28 days, patients must discontinue protocol therapy.

8.4.7 Skin Reactions

Worst Toxicity	Management*
Grade 1	Maintain dose level
Grade 2	
Tolerable maculopapular rash:
 
 Initiate/intensify appropriate skin toxicity therapy, e.g. with topical steroids BID and oral antihistamines. Maintain dose level. 
Intolerable maculopapular rash:
 
 Omit dose and initiate/intensify appropriate skin toxicity therapy, e.g. with topical steroids BID, oral antihistamines and oral steroids if required*. 
First occurrence:
 
 If resolved to grade \leq 1 in $<$ 2 weeks, maintain dose level. If resolved grade \leq 1 in more than 2 weeks, reduce 1 dose level. Consider continuing skin toxicity therapy up to 2 weeks after re-introduction of buparlisib. In case of flare after cessation of skin toxicity therapy, consider prompt reimplementation. 
Second occurrence: omit dose and follow treatment guidance above.
 
 Once resolved to grade \leq 1, reduce 1 dose level**.
Grade 3	Omit dose until resolved to \leq grade 1 then decrease one dose level**
Grade 4	Discontinue buparlisib

* Co-medicate as appropriate with antihistamines, topical or oral steroids (patients requiring high dose steroids may become inevaluable for response assessment), moisturizers, sunscreen. In addition for acneiform rash consider topical or oral antibiotics and bacterial swab if infection suspected.

** After treatment is resumed at a lower dose, if the same toxicity recurs with the same severity, then the next treatment should be resumed at a lower dose regardless of duration. If the same toxicity occurs with a worse severity, then the patient must discontinue treatment with buparlisib.

If a third dose reduction is required, patients must discontinue protocol therapy.

If therapy is delayed by $>$ 28 days, patients must discontinue protocol therapy.

8.4.8 Other Non-Hematological Adverse Events, Including Diarrhea

Worst Toxicity	Management
Grade 1	Maintain dose level
Grade 2	Symptomatic management*; continue dosing with no change. For persistent grade 2 effects, investigator may decrease by one dose level
Grade 3 **	Omit dose*** until resolved to \leq grade 1 then decrease one dose level****
Grade 4	Permanently discontinue buparlisib

* For buparlisib induced diarrhea, standard treatment including prompt commencement of loperamide is recommended alongside rehydration (can refer to Recommended Guidelines for the Treatment of Cancer Treatment-Induced Diarrhea, [Benson 2004]).

** Omit for grade 3 nausea or vomiting only if it cannot be controlled with optimal anti-emetics.
Omit for fatigue only if significant worsening from baseline (investigator discretion).

*** Patients requiring treatment hold for >28 days will discontinue protocol therapy.

**** After treatment is resumed at a lower dose, if the same toxicity recurs with the same severity, then the next treatment should be resumed at a lower dose regardless of duration. If the same toxicity occurs with a worse severity, then the patient must discontinue treatment with buparlisib.

8.5 Duration of Therapy

Treatment will continue until the criteria for removal from protocol treatment have been met (see section 12.0).

8.6 Concomitant Therapy

Permitted:

- Other supportive and palliative care (e.g. pain control) as required throughout the study.
- Anti-emetics or anti-diarrheal agents as required.
- Growth factors may be used according to centre policy.
- Low molecular weight heparin if indicated.

Permitted with caution:

- CYP450 substrates other than strong CYP3A4 inhibitors and inducers (see Appendix VII).
- Drugs with possible or conditional risk of inducing Torsades de Pointes (see Appendix VIII).

Not permitted:

- Strong CYP3A4 inhibitors and inducers (see Appendix VII).
- Drugs with known risk to induce Torsades de Pointes (see Appendix VIII).
- Warfarin.
- Other anti-cancer therapy or investigational therapy.

Details of any concomitant medications given should be recorded on the appropriate Electronic Case Report Form.

Infections including Pneumocystis Jiroveci pneumonia (PJP) and cytomegalovirus (CMV) reactivation have been observed in patients with CLL treated with alternate PI3 kinase inhibitors. Opportunistic infections have not been associated with buparlisib therapy to date. Physicians should remain vigilant and investigate as clinically appropriate in event of fever or respiratory symptoms. Prophylaxis can be considered in those at high risk at investigator discretion.

9.0 EVALUATION DURING AND AFTER PROTOCOL TREATMENT

All patients entered on study must be evaluated according to the schedule outlined in Appendix I with documentation submitted according to the schedule in Appendix IV.

9.1 Evaluation During Protocol Treatment

[figure not shown]
Investigations		Timing		
History and Physical Exam including:	
 History Weight ECOG Performance status Blood pressure and pulse Clinical tumour / organomegaly measurements (if applicable) 	Day 1 each cycle		
Hematology ¹	CBC, differential (including lymphocytes)			
Biochemistry ¹	
 
  
 creatinine potassium bilirubin (fractionated if known Gilberts) LDH AST, ALT 	 
 calcium albumin glucose (fasting)⁵ phosphate⁶ uric acid⁶ lipase 	
 
	
 creatinine potassium bilirubin (fractionated if known Gilberts) LDH AST, ALT 	
 calcium albumin glucose (fasting)⁵ phosphate⁶ uric acid⁶ lipase 	Days 1 and 14 cycle 1 and 2 ² Day 1 each cycle thereafter ² Tumour lysis monitoring on days 1, 2, and 3 of cycle 1 required only in first 4 patients treated, see below ⁶

 creatinine potassium bilirubin (fractionated if known Gilberts) LDH AST, ALT 	
 calcium albumin glucose (fasting)⁵ phosphate⁶ uric acid⁶ lipase 			
Radiology ³	
 CT scan of neck, chest, abdomen and pelvis 	
 To be repeated 8, 16, and 24 weeks from registration and thereafter every 12 weeks⁷. At time PR or CR criteria are otherwise met and 8 weeks after PR or CR to confirm. 		
Assessment for Minimal Residual Disease (MRD) (Optional)	
MRD assessment either by:
 
 4-color Flow Cytometry (MRD Flow) or Allele Specific Oligonucleotide PCR on peripheral blood or Flow cytometry or immunohistochemistry on bone marrow 	Desirable if CR criteria otherwise met, but optional.		
Bone Marrow	
 Bone marrow aspirate and biopsy 	At time other criteria for CR first met and 8 weeks later to confirm sustained CR or if cytopenia of uncertain cause.		
Correlative blood work	
 Whole blood processed as per Section 17 and Laboratory Manual 	At time of disease progression (if applicable)		
Mood Questionnaire	
 Patient self-rating mood scales for depression (PHQ-9) and anxiety (GAD-7) 	Days 1 and 14 cycle 1 and 2, Day 1 of each cycle thereafter and end of treatment visit		
